9.4 Power and Sample Size

Primary Aim: Review of the literature suggests that the incidence of GI aGvHD ranges from 15% to 45% across various studies; therefore a precise estimate of baseline GI aGvHD incidence for this study population is not available. The incidence of GI aGvHD was 27% in the control arm of the most recent COG trial (ASCT0431), which enrolled a patient population where 54% of patients received grafts from matched sibling donors. We anticipate a higher rate of GI aGvHD in the control arm of this trial, as we are including only alternative donor recipients (refer to eligibility criteria), and therefore project the baseline cumulative GI aGvHD incidence through Day 120 to be at least 30%. Success will be defined as a 40% relative reduction in the cumulative incidence of GI aGvHD (i.e., 18% in LBP arm vs. 30% in placebo arm). A sample size of 120 (60 per arm) for the screening stage and 454 (227 per arm) for the confirmatory stage (including patients randomized during the screening stage) will provide 85% power to detect an effect size of 40% relative reduction at 1-sided $\alpha=0.3$ and 0.05, respectively in a two-sample test of binomial proportions. The overall power of the study, which is the probability of establishing efficacy in the primary endpoint in both analyses, is lower than the power for each component separately and higher than the product of two. Based on simulations, the overall power is at 80% in this scenario. The overall type I error for the design is also slightly reduced from the type I error of 0.05 for each individual component if they are analyzed separately. Based on simulations, the overall type I error is at 0.035.

Exploratory Aims 1 and 2: The sample size for the primary aim drives the overall accrual goal and thus the number of subjects available for the exploratory aims. These endpoints will be analyzed only at the end of the study, either at the end of the screening stage or confirmatory stage. Therefore, the power is estimated for the two situations separately based on sample size of 120 (60 per arm) or 454 (227 per arm) without any adjustment for power after the confirmatory stage. For Exploratory aim #1, a baseline rate of Grade II–IV aGvHD in the range of 30%–50%, the sample size after confirmatory stage is sufficient to detect a 15% reduction in aGvHD rate, while the sample size after screening stage is sufficient to detect a 20% reduction in aGvHD rate with LBP compared to placebo. Power estimation is based on 2-sample test of proportions at $\alpha=0.05$ (2-sided). For Exploratory aim #2 on serum citrulline levels, the sample size after confirmatory stage is sufficient to

detect an effect size of 0.4 standard deviation (SD), assuming we obtain samples from 80% or more of the subjects; on the other hand, the sample size after screening stage is sufficient to detect an effect size of 0.7 SD if we obtain samples from $\geq 80\%$ subjects. Power estimation is based on two-sample t-test at $\alpha=0.0125$ (2-sided), where α is based on the Bonferroni adjustment for the 4 parallel comparisons with an overall $\alpha=0.05$.

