9.3 Data Analytic Plan

Preliminary Descriptive Analysis: Study variables will be summarized using simple descriptive statistics such as count/percentage for categorical variables and mean/standard deviation/median/interquartile range for continuous variables. Baseline patient demographics and clinical characteristics will be summarized. The two arms will be balanced on the factors included in the stratified randomization. Treatment arms will be descriptively compared for other potential confounders for possible inclusion in the multivariate models. Arm comparison will be performed using simple two-sample tests, such as χ^2 test of proportions for categorical variables and independent t-tests or Wilcoxon rank sum tests for continuous variables. Analyses for each of the aims is presented below:

Primary Aim: The primary aim is to determine whether oral *LBP* prevents the development of Stage 1-4 GI aGvHD incidence in children and adolescents undergoing alloHCT. We hypothesize that administration of oral *LBP* will reduce the incidence of Stage 1-4 GI aGvHD compared to placebo. As described above, accrual will be conducted in two stages, the screening stage and the confirmatory stage. The proportion of 120 centrally reviewed, eligible and evaluable randomized patients who received at least 1 dose of treatment having Stage 1-4 GI aGvHD incidence from Day 0 through Day 120 will be compared between the two arms after the screening stage via two-sample unpooled chi-square test of proportions at 1-sided $\alpha=0.3$. If this liberal estimate of efficacy of *LBP* is demonstrated, accrual of the confirmatory stage will continue.

At the end of the confirmatory stage, the proportion of eligible patients having Stage 1-4 GI aGvHD incidence from Day 0 through Day 120 will be compared between the two arms (including patients randomized in both stages) via two-sample unpooled chi-square test of proportions at $\alpha=0.05$ (1-sided). We will use a modified intention-to-treat approach for the primary analysis.

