9.5 Interim Monitoring

Study data will be reviewed by DSMC twice a year during the first 2 years of study activation, and once a year thereafter if no concerns are identified.

The study will be conducted in two stages: a randomized *screening* stage, and a larger *confirmatory* stage. The screening stage will compare the proportion of Stage 1-4 GI aGvHD between the 2 arms. The proportion of 120 centrally reviewed, eligible and evaluable randomized patients having Stage 1-4 GI aGvHD incidence from Day 0 through Day 120 will be compared between the two arms via two-sample test of proportions at 1-sided $\alpha=0.3$. If the screening stage suggests efficacy ($p<0.3$), the study will proceed to the confirmatory stage ($N=454$). If efficacy is not established at the screening stage, the data will be referred to the COG Data Safety and Monitoring Committee (DSMC) for consideration of early termination.

Amendment 1: Haploidentical transplantation in children has increased over the past few years. Although single institution studies have demonstrated a remarkably lower acute and chronic Graft vs Host Disease incidence and severity, these results have not been duplicated in larger multicenter trials. In these multicenter trials, the Grade II-IV Acute GvHD rate does not appear to be significantly different from that of other alternative donor trials. While we do agree that the rate of chronic GVH appears much less, our current study ends at Day + 120 and thus chronic GVH is not measured in this trial.

Therefore, it is presumed to have no impact on the power for the primary aim by having haploidentical patients enrolled in this study. The estimated primary outcome rate aGvHD and proportion of haploidentical patients will be monitored bi-annually. At each monitoring time, by assuming the observed aGvHD rate, proportion of haploidentical patients within the control arm, and using the same power simulation (that we've used to provide power analysis for the protocol), if the estimated power at the end of the study is less than 80%, we will adjust the sample size through an Amendment. All observed rates will be available only for members of DSMC to review.

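### Section 9.4 gives the final test 85% power, but 227 per arm at one-sided 0.05 has about 92%; the stated 80% overall fits 92%, not 85%

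*Combined protocol and SAP*

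**What the plan says.** Section 9.4 (Power and Sample Size, Primary Aim) plans for "18% in LBP arm vs. 30% in placebo arm". It sets 60 per arm for the screening test at one-sided alpha 0.3 and 227 per arm for the final test at one-sided 0.05. It attaches a single power to both: "454 (227 per arm) for the confirmatory stage (including patients randomized during the screening stage) will provide 85% power".

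The same paragraph defines overall power, "which is the probability of establishing efficacy in the primary endpoint in both analyses", and reports two simulated results: "Based on simulations, the overall power is at 80% in this scenario" and "Based on simulations, the overall type I error is at 0.035".

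Section 9.3 (Data Analytic Plan, Primary Aim) confirms the final test as a "two-sample unpooled chi-square test of proportions at $\alpha=0.05$ (1-sided").

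**The concern.** The two tests address the same pair of rates with very different sample sizes and alphas. They could share one power figure, but that has to be checked. Here it holds for the screening test only.

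This matters for two reasons:

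- **Which alpha governs the primary test.** A reader who checks 85% against 227 per arm recovers one-sided 0.025, not the stated 0.05. Section 9.4 also uses two-sided alphas for the exploratory aims, so the doubt is a natural one.
- **Power is used during the trial.** Section 9.5 re-estimates power twice a year with the simulation used for the protocol, and calls for a sample-size amendment if it falls below 80%. Anyone who checks that simulation against 9.4 will find that the final-test figure does not agree, and may wrongly suspect the simulation or the alpha.

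**Working it through.** **Inputs.** Placebo rate 0.30, LBP rate 0.18, 60 and 227 per arm, one-sided alphas 0.30 and 0.05 (all 9.4); 1:1 allocation (9.2); unpooled test (9.3). The 227 per arm includes the 60 from screening.

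**1. Power of each test (unpooled).**

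Power = Φ(d / SE − z), with d = 0.30 − 0.18 = 0.12 and SE = √[(0.30×0.70 + 0.18×0.82)/n] = √(0.3576/n).

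- Screening, n = 60: SE = 0.0772, d/SE = 1.554, z = 0.524. Power = Φ(1.030) = **84.8%**. This reproduces the stated 85%.
- Final, n = 227: SE = 0.0397, d/SE = 3.023, z = 1.645. Power = Φ(1.379) = **91.6%**. The stated 85% is not reproduced.
- Final at one-sided 0.025, n = 227: z = 1.960. Power = Φ(1.063) = 85.6%.

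**2. Other versions of the test.**

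| Version | 60 per arm, 0.30 | 227 per arm, 0.05 | 227 per arm, 0.025 |
|---|---|---|---|
| Unpooled normal | 84.8% | 91.6% | 85.6% |
| Pooled normal | 84.7% | 91.3% | 85.2% |
| Unpooled test, exact enumeration | 84.6% | 91.5% | 85.6% |
| Continuity-corrected (pooled) | 79.1% | 89.5% | 82.5% |
| Fisher's exact | 78.8% | 89.6% | not run |

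At the stated alphas, no version gives 85% for the final test. The two conservative versions also lose the 85% at screening.

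**3. Overall power as a cross-check.**

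The two test statistics have correlation √(60/227) = 0.514. Overall power is the bivariate normal probability that both tests succeed.

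| Component powers | Overall power |
|---|---|
| 85% and 85% (as written) | 75.9% |
| 84.8% and 91.6% (final alpha 0.05) | 80.3%; exact 80.0% |
| 84.8% and 85.6% (final alpha 0.025) | 76.2%; exact 76.0% |
| **Stated in 9.4** | **80%** |

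**4. Overall type I error.**

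- Final alpha 0.05: 0.0364 by bivariate normal; 0.0365 to 0.0371 by exact enumeration over null rates of 18% to 30%.
- Final alpha 0.025: about 0.020.
- Stated: 0.035. This is close to the first and far from the second. It is not matched exactly, and the number of simulation runs is not given. If there were 1,000 to 10,000 runs (my assumption), 0.035 lies 0.35 to 1.1 standard errors below 0.0371.

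So the plan's simulation is consistent with a final one-sided 0.05, and the 85% for the final test is the figure that does not fit.

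**5. What 85% would need.**

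n = (1.645 + 1.036)² × 0.3576 / 0.12² = 178.5, so 179 per arm (181 pooled). Overall power would then be about 76.5%. The 227 per arm therefore fits the 80% overall target, not an 85% target for the final test.

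**The case against.** **It has no consequence.** The error understates power. The design rests on the simulated 80% and 0.035, which the check supports, and the 9.5 trigger uses 80%. All of this stands, and it is why this is a correction of the text and not of the design. It does not make the sentence true.

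**85% may be meant as a minimum.** The sentence states a value, while the same paragraph says "at least" for the control rate where it means a floor.

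**85% may allow for losses.** Section 9.1 adds the 10% allowance on top of 454, up to 500. Even 204 per arm would give 88.6% (pooled).

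**The paragraph does not contradict itself on its face.** It says only that overall power lies between the product and the single powers. For two 85% tests that range is 72.3% to 85%, which contains 80%. This is correct: the conflict appears only once the correlation of 0.514 is used.

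**The analysed rates may be higher than 30% and 18%.** Section 9.2 counts patients lost or dead before their outcome is known as events. If 2% to 6% were imputed equally in both arms (an assumption), final power would be 89.5% to 85.0%. Screening power would then fall to 83.3% to 80.3%, so no single value gives 85% for both, and 9.3 expects few such patients. What stands is that 92% should be quoted for rates of 30% and 18% as analysed.

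**A 0.025 calculation is speculation.** The documents do not say where 85% came from. The match is an inference, and both sections state 0.05.

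**Conclusion.** The concern holds. At 30% against 18%, with 227 per arm and one-sided 0.05, the final test has 91.3% to 91.6% power, not 85%. The 85% is right for screening only. The stated overall 80% is correct and agrees with about 92% for the final test; two tests with 85% power each would give 75.9%.

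The error is conservative. It does not affect the sample size, the alpha levels, the stage rule or the analysis.

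The final-test figure needs no assumption beyond the plan's own inputs. The two-stage figures assume that the trial stops if screening fails. Section 9.5 says only that in that case "the data will be referred to the COG Data Safety and Monitoring Committee (DSMC) for consideration of early termination". If the trial went on regardless, overall type I error would be about 0.050.

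**What to change.** In 9.4, replace the single 85% by three figures for 30% against 18%: about 85% for the screening test, about 92% for the final test and 80% overall. The cost is one sentence; nothing in the design or analysis changes.

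Only if one-sided 0.025 was in fact intended for the final test would 9.3 and 9.4 need a corrected alpha, with overall power restated as about 76% and overall type I error as about 0.020. The stated 80% and 0.035 argue against that.

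Optional, and separate from this error: say in 9.5 that the 80% criterion means overall two-stage power with the 40% relative reduction held fixed.

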For stage 4 GI: the term “severe abdominal pain” will be defined as:

- (a) Pain control requiring institution of opioid use, or an increase in on-going opioid use, PLUS
- (b) Pain that significantly impacts performance status, as determined by the treating MD.

If colon or rectal biopsy is +, but stool output is < 500 mL/day (< 10 mL/kg/day), then consider as GI stage 0.

There is no modification of liver staging for other causes of hyperbilirubinemia

Overall Clinical Grade (based on the highest stage obtained):

Grade 0: No stage 1-4 of any organ

Grade I: Stage 1-2 skin and no liver or gut involvement

Grade II: Stage 3 skin, or Stage 1 liver involvement, or Stage 1 GI

Grade III: Stage 0-3 skin, with Stage 2-3 liver, or Stage 2-3 GI

Grade IV: Stage 4 skin, liver or GI involvement

Table 2 Evaluating Liver GVHD in the Absence of Biopsy Confirmation (See Table 3.0 below)

Establishing liver GVHD with no skin or GI GVHD

No Skin/GI GVHD Day 0-35	Assume no liver GVHD, unless proven by biopsy	
No Skin/GI GVHD Day 36-100	If NO other etiology identified, NO improvement with stopping hepatotoxic medications/TPN: Stage as liver GVHD	If other etiology identified or improves with stopping hepatotoxic drugs/TPN: Do not stage as liver GVHD

Establishing liver GVHD with skin or GI GVHD and other cause of hyperbilirubinemia

Skin and/or GI GVHD present	Worsening bilirubin level (includes worsening just prior to onset of skin or GI tract GVHD) OR stable elevated bilirubin despite resolution of non-GVHD cause of increased bilirubin: Stage as liver GVHD	Stable or improving bilirubin after diagnosis of skin or GI GVHD, irrespective of treatment: Do not stage as liver GVHD
------------------------------------	---	---

Changing liver GVHD stage with other cause of hyperbilirubinemia

Skin and GI GVHD stable, improving, or absent	Liver GVHD staging is carried forward without increase in stage until other disease process resolves (e.g., if TTP is diagnosed in the presence of stage 2 liver GVHD, the liver GVHD stage 2 is carried forward despite rising bilirubin level until TTP is resolved. If there is no liver GVHD – stage 0 – and new onset TTP, the stage 0 is carried forward until TTP is resolved).
--	--

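### Section 9.4 gives Aim 1 power at N=120 as if that were a free-standing trial, but a planned end at 120 follows a failed GI screen on a nested endpoint

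*Combined protocol and SAP*

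**What the plan says.** Section 9.4 states when Aims 1 and 2 are analysed: "These endpoints will be analyzed only at the end of the study, either at the end of the screening stage or confirmatory stage". It estimates power for the two possible endings separately, "based on sample size of 120 (60 per arm) or 454 (227 per arm) without any adjustment for power after the confirmatory stage". For Aim 1, with placebo Grade II–IV rates of 30% to 50% and a two-sided 0.05 test, it says that "the sample size after screening stage is sufficient to detect a 20% reduction in aGvHD rate with LBP compared to placebo". No power level is attached to that statement.

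The ending is decided by the primary endpoint. Sections 9.2 and 9.5 continue to 454 if the GI screen on the first 120 patients gives one-sided p<0.3. Otherwise, "If efficacy is not established at the screening stage, the data will be referred to the COG Data Safety and Monitoring Committee", which considers early termination.

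Appendix III links the two endpoints through the overall grade: "Grade II: Stage 3 skin, or Stage 1 liver involvement, or Stage 1 GI". Stage 2–3 GI is Grade III and Stage 4 GI is Grade IV.

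For the primary endpoint, section 9.4 does carry the gate through: "The overall power of the study, which is the probability of establishing efficacy in the primary endpoint in both analyses" is given as 80% from simulation.

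**The concern.** These provisions do not fit together for Aim 1. If the trial ends at 120 by its efficacy rule, the GI comparison in those 120 patients has already shown little or no benefit. Every GI event is also an Aim 1 event, so the Grade II–IV difference in the same patients has been selected to be small. The sufficiency statement describes an unselected 120-patient trial, and the efficacy rule does not lead to one.

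What is at stake is how a stop at 120 would be read. A non-significant Grade II–IV result beside a failed GI screen could look like independent confirmation, when much of it would be the same events counted again. A statement that the sample was sufficient would encourage that reading. Correcting only the unconditional power at 60 per arm would leave the problem in place.

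**Working it through.** **Inputs from the documents.** 60 and 227 per arm, 1:1 allocation; GI aGvHD 30% vs 18% (9.4); GI literature range 15% to 45% (9.4); screen by unpooled two-proportion test at one-sided 0.30 (9.3); Aim 1 at two-sided 0.05 (9.4); nesting of GI events in Grade II–IV (Appendix III). Missing outcomes count as events for both endpoints (9.2), which keeps the nesting.

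**Assumptions.** The 20% reduction is read as 20 percentage points; read as relative, power at 60 per arm is only 11–19%. The documents do not give the split of Grade II–IV disease into GI and non-GI parts, so several GI rates are shown.

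**1. The plan's own figures.** Screen: SE = √[(0.30×0.70 + 0.18×0.82)/60] = 0.0772. Power = Φ(0.12/0.0772 − 0.524) = Φ(1.03) = 85%, as stated. Simulating both stages gives joint primary power of 80.0%, as stated. (The same model gives about 91% for the 454-patient primary test taken alone, against the stated 85%. That is a separate matter.)

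**2. Aim 1 at 60 per arm, ignoring the gate.** Power = Φ{[δ − 1.96√(2p̄(1−p̄)/60)] / √[(p₁(1−p₁)+p₂(1−p₂))/60]}. For 40% to 20%: (0.20 − 1.96×0.0837)/0.0816 = 0.44, so 67%. Exact enumeration with the pooled test gives 68% (40 to 20), 64% (45 to 25) and 62% (50 to 30).

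**3. Aim 1 at 60 per arm, given a failed screen.** Per arm, GI events are Bin(60, p_GI), and Grade II–IV events are GI + Bin(60 − GI, (p_T − p_GI)/(1 − p_GI)). With nesting, the two marginal rates fix the joint distribution. Enumerating all outcomes with unpooled GI z ≤ 0.524, pooled Aim 1 test, true reduction 20 points:

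| GI, placebo vs LBP | Screen fails | Grade II–IV scenarios | Power given failure | Mean estimate (points) |
|---|---|---|---|---|
| 45% vs 27% | 5.5% | 50→30 | 0.1% | 3.6 |
| 30% vs 18% | 15.4% | 40→20, 45→25, 50→30 | 8.4%, 12.8%, 17.0% | 9.2, 10.0, 10.8 |
| 30% vs 24% | 41% | 45→25, 50→30 | 27%, 30% | 13.2, 13.8 |
| 15% vs 9% | 29% | 40→20, 45→25, 50→30 | 41%, 40%, 40% | 14.6, 15.0, 15.4 |
| 30% vs 30% | 69% | 50→30 | 46% | 16.3 |
| 15% vs 15% | 70% | 40→20, 45→25, 50→30 | 57%, 53%, 52% | 17.3, 17.5, 17.7 |

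Scenarios are left out where nesting rules them out. With GI at 18% on LBP, Grade II–IV on LBP cannot be below 18%, so a 20-point drop needs a placebo rate of at least 18 + 20 = 38%. The 30% low end of the plan's Aim 1 range therefore cannot be combined with its own GI assumption.

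**4. The whole two-stage rule.** Taking every failed screen as a stop at 120, power = P(pass)×power(454 | pass) + P(fail)×power(120 | fail). For GI 30% vs 18% and a 15-point reduction from 50% to 35%: 0.846×0.923 + 0.154×0.059 = 0.79. Across 35→20 to 50→35 the result is 79–82%, against 90–95% for a fixed 454.

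**The case against.** The strongest reply is that section 9.4 states its method: nominal sample-size statements, made separately for two endings, for an exploratory endpoint that triggers no decision. No power level is attached, so no stated number is shown to be wrong. That stands. The fault is that the statement describes a design property the trial lacks.

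Three stronger readings are tempting, and the documents do not support them.

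- **That power at 120 is simply 8–17% and the effect is halved.** Those figures belong to GI 30% vs 18%, where the screen fails only about 15% of the time, so they describe a case in which stopping at 120 is unlikely. The 8% end also needs non-GI disease to fall from 10% to 2%, an 80% cut against 40% for GI; at 50 to 30 it falls from 20% to 12%, the same 40%. At GI 15% vs 15% the shortfall is only about 10–11 points.
- **That an analysis at 120 can only follow a failed screen.** Failure leads to DSMC consideration, not automatic stopping, and section 12.2 lets the DSMC recommend termination on toxicity as well. The figures above are power given a failed screen; the DSMC's further judgement is not modelled.
- **That the plan calls the N=120 estimate unbiased, or would take a null result as showing no effect.** It says neither. The risk is one of interpretation.

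After a passed screen there is no loss: power at 454 rises slightly, from 93% to 95% for 40% to 25%.

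**Conclusion.** The concern holds in this form. The planned efficacy route to an Aim 1 analysis at 120 runs through a failed GI screen on a nested endpoint, and the sufficiency statement ignores it. In every scenario run with a true 20-point reduction, power given failure is below the ungated value and the mean estimate is below 20 points. Over the GI rates examined, which span the literature range that the plan cites, conditional power runs from near 0% to 57%, against 62–68% ungated. At the plan's own GI rates it is 8–17%, with a mean estimate of 9–11 points.

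The direction follows from the documents. The size rests on the assumed GI/non-GI split, on reading the reduction as absolute, and on placebo rates of 40–50%. The point concerns a power statement and the reading of an exploratory result; the primary test, its alpha and its sample size are not affected.

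**What to change.** In section 9.4, replace the N=120 sufficiency statement for Aim 1 with wording to this effect: a planned Aim 1 analysis at 120 follows a failed GI screen in the same patients; because Stage 1–4 GI aGvHD is contained in Grade II–IV aGvHD, the result is biased towards no difference; it is descriptive, is reported with a confidence interval, and is not evidence of no effect.

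Beside it, give Aim 1 power conditional on a failed screen over a stated range of GI rates, with the GI/non-GI assumption named, instead of one range. Add Aim 1 power for the whole two-stage rule (about 79–82% for a 15-point reduction at GI 30% vs 18%). Single-stage figures may stay if labelled as ignoring the gate. Say whether the reductions are absolute, and reconcile the 30% placebo rate with the 18% GI rate on LBP.

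The cost is one wording change and extra output from the existing power simulation, with no added patients or procedures. The downside is a less favourable stated power for the exploratory aim.
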